## 7.2 Technology Transfer

This protocol has no associated patents, CRADAs or CTAs.

## 7.3 Tissue Studies of Pathogenesis of Oral Chronic GVHD

### 7.3.1 Immune cell kinetics in the oral tissues

Microscopic examination of the H&E stained tissue sections will be performed in the Laboratory of Pathology. Oral chronic GVHD grade will be determined based on the following criteria:

1. Number/percentage of the dyskeratotic cells
2. Number/percentage of the intraepithelial lymphocytes
3. Degree of the basal cell layer destruction
4. Degree of the subepithelial lymphocytic infiltrate

Immune cell infiltrate will be characterized by immunohistochemistry and laser scanning cytometry using appropriate markers for T-cell subsets (CD3, CD4, CD8), NK cells (CD16, CD56) and dendritic cell subsets (CD1a, CD11c, CD123, CD205/DEC-205, CD207/Langerin, CD209/DC-SIGN, BDCA-2, 4). Apoptosis will be assessed by immunohistochemical staining of the cells for apoptotic markers (e.g. caspase 3). Laser scanning cytometry allows precise quantitative evaluation of different cell populations in the tissue sections by analogy with flow-cytometry and has been used successfully to characterize immune cell infiltrates [27].

We are particularly interested in the role of peripheral tissue dendritic cells in chronic GVHD. The role of dendritic cells in induction of peripheral tolerance has received considerable attention in the recent literature. For example, plasmacytoid dendritic cells (pDCs) have been suggested to drive Th2 responses and promote induction of T-regulatory cells [28, 29]. The role of plasmacytoid dendritic cells in chronic GVHD is unclear. Studies of association of peripheral blood pDCs with cGVHD rendered conflicting results [30, 31]. pDCs have been reported to be present in small numbers in the normal skin and increase in certain inflammatory conditions [32]. The relative numbers and function of different dendritic cell subsets in the tissues in chronic GVHD setting has not been investigated.

Corticosteroids have been shown to interfere with dendritic cell maturation [24]. Keeping dendritic cells in an immature state could be advantageous in the peripheral tissues, because the immature DCs have been shown to play a key role in induction of tolerance [25]. Dexamethasone has been shown to induce IL-10 producing DCs which may potentially induce tolerance to peripheral tissue antigens [26].

Additionally, we will assess the degree of chimerism of keratinocytes, antigen-presenting cells and lymphocytes in tissue sections. Data from the transplantation literature suggests that transplanted donor cells are capable of stable integration into the recipient tissues [33, 34]. Integration of donor cells into the peripheral tissues has the potential to affect the antigenic repertoire. It is unclear to what degree such “in-situ” chimerism could affect the development of tolerance or conversely – graft versus host disease. We hypothesize that increased donor chimerism of peripheral tissues could facilitate establishment of tolerance to recipient tissue antigens by analogy with organ transplants, where increased population of donor organs by recipient cells is thought to be partially responsible for long-term tolerance to transplanted organs. Adult mesenchymal stem cells have been demonstrated to migrate to the sites of tissue damage and integrate into the tissues [35]. Mesenchymal stem cells have been shown to possess immunomodulating and tolerogenic properties and may play a role in tolerance induction in peripheral tissues of the recipient [36]. Although, studies have shown that mesenchymal stem cells in the bone marrow of the transplant recipients are of the host origin, it is possible that the infused donor mesenchymal stem cells populate peripheral tissues and change their phenotype. We plan to investigate three types of cell populations in oral tissues, namely keratinocytes, antigen presenting/Langerhans cells, and lymphocytes for degree of chimerism and correlate the findings with the clinical and histopathological severity of GVHD. Briefly, tissue sections will be stained by immunohistochemistry for appropriate cell markers and the pure cell populations will be dissected by laser capture microdissection. After isolation of DNA, we will perform PCR for short tandem repeats (STR) of the selected locus and analyze the fluorescent PCR products using capillary sequencer. This method has an advantage of high sensitivity and is independent of donor-recipient gender mismatch[37].

### 7.3.2 Gene expression profiles (because oral biopsies are optional, samples will not be available for all subjects)

Biopsied oral mucosal tissue will be sectioned and part prepared for the gene array analysis. Six (6)  $\mu$ m thick cryostat frozen sections will be prepared and stored at -80°C. Prior to RNA extraction, the keratinocyte layer will be separated from the underlying layers by laser capture microdissection.

Additionally, a 2 mm thick layer of the underlying tissue will also be dissected. This will allow us to take into account different tissue thickness in the oral mucosal biopsies and enrich for keratinocytes and immune cells. The two layers will be assayed separately. We will use focused, pathway specific arrays (Superarray, Superarray Bioscience Corporation, Frederick, MD) for gene array studies. Specifically, arrays focused on apoptosis, dendritic cells/antigen presentation, cytokines, and chemokines/adhesion molecules will be used. The use of smaller, more focused arrays decreases the statistical problems associated with multiple testing and simplifies data analysis. The most interesting and significant findings will be validated by PCR and protein based assays, such as immunohistochemistry and ELISA. These samples will not have direct subject identifiers.

### 7.3.3 Histopathologic diagnosis of oral cGVHD

In the setting of subclinical tissue changes including absence of inflammation or lichenoid hyperkeratosis, positive histopathologic findings (lichenoid interface lymphocytes with exocytosis and variable apoptosis), have been noted in the baseline oral buccal mucosal biopsies in this study. This phenomenon has been noted in the literature [38-40], however, the diagnostic and prognostic value of this finding has not been reported. This sub-study will use all available baseline oral biopsies from 07-H-0005 to address this question.

#### 7.3.3.1 Re-evaluation of the baseline histopathologic findings of patients in protocol 07-H-0005

Scanned, de-identified images of the H&E slides will be sent to four pathologists with extensive experience in evaluating oral GVHD to individually evaluate all baseline oral biopsies from 07-H-0005. No identifiable patient or clinical information will be shared with the pathologists beyond the general time post-transplant (approximately 90 days) and the reason for the biopsy (protocol baseline). All files will be mailed on a compact disc to the individual pathologist, to be viewed using the Aperio digital pathology viewer software and scored using a standard matrix (Appendix F).

This data will be collected from the pathologists and will be used to calculate

- Inter-rater reliability of the pathologists for oral cGVHD diagnosis
- Incidence of cGVHD diagnostic features in the absence of clinical signs, along with the individual histopathologic features most common in the oral mucosa in the early post-transplant period

This pathology data will then be combined with clinical data, including pre-transplant conditioning regimen, chemotherapy and irradiation history, and any incidence of acute or chronic GVHD to determine the clinical significance and the negative and positive predictive value of this histopathologic finding.

## 7.4 Salivary and Plasma Proteomics

We hypothesize differential expression of salivary and plasma proteins before and after GVHD development. GVHD specific biomarkers would be potentially useful for predictive and prognostic purposes. It may also provide insight into the biology of the disease as manifested in the oral cavity. We will also compare the salivary protein expression profiles to those from other autoimmune conditions with similar presentation such as Sjogren's syndrome.

We will use surface enhanced laser desorption/ionization – time of flight (SELDI-TOF) mass spectrometry (MS) to investigate screen for differences in protein expression in whole saliva. SELDI-TOF MS Protein Chip technology has been used extensively for biomarker mining and proteomic pattern determination on various body fluids including plasma, urine, and saliva [41, 42]. It uses various affinity surfaces (protein chips) to selectively bind the proteins of interest from the sample. The absorbed proteins are then ionized by a laser shot and the resulting ions accelerate over a certain distance in the mass spectrometer. The time of flight of each ion can be measured and is inversely proportional to the mass of the protein ion. This information in the form of flight times and ion current intensity can be collected, displayed graphically in the form of intensity peaks, and later analyzed by bioinformatic software. Expression differences detected by this high throughput method can be validated using traditional antibody based assays.

Additionally, we will use 2-dimensional difference in gel electrophoresis (2D-DIGE) to further evaluate the salivary and plasma protein expression before and after development of GVHD. This method is complementary to SELDI-TOF in that it has better accuracy for higher molecular weight proteins [43]. Differentially expressed protein spots on a gel can be excised and protein identity determined by mass spectrometric sequencing. The results of the proteomic studies will be used for hypothesis generation for future investigations.

### **7.5 Oral Bacterial Colonization**

We will evaluate the oral bacterial flora changes associated with development of chronic GVHD by broad range bacterial 16S rDNA PCR. This sensitive methodology allows simultaneous testing of multiple, including non-cultivable, bacterial strains and has been used for microbiological surveillance in various mucosal sites [44]. The important role that bacteria play in maintenance of local homeostasis has been demonstrated in several conditions in which disease phenotype is associated with profound shift from “health-associated” to “disease-associated” flora [45]. The pathogenesis of other conditions, such Crohn’s disease has been linked to loss of tolerance to normally harmless commensal bacteria with inappropriate inflammatory response [46]. Within the GI tract, dendritic cells constantly sample the antigens from the lumen of the gut and present them to naïve T-cells in the Peyer’s patches and mesenteric lymph nodes inducing tolerance to commensal bacteria and immune responses to pathogens [47]. It is possible that a similar mechanism operates in oral tissues.

## **8. BIOSTATISTICAL CONSIDERATIONS**

### **8.1 Hypothesis**

#### **8.1.1 Primary hypothesis**

Our primary hypothesis is that dexamethasone oral rinse 0.5 mg/5 ml administered 3 times a day for 2 minutes will decrease the incidence of clinically significant oral chronic GVHD (primary endpoint) over the three month treatment period.

#### **8.1.2 Secondary hypotheses**

Our secondary hypothesis is that the dexamethasone group will have significantly lower oral GVHD scores as measured by the GVHD Severity Scale and The Lichen Planus Severity Scale (Appendix B and C). We also hypothesize that prophylactic use of topical dexamethasone will improve oral health specific and general quality of life (QOL) as measured by the corresponding QOL instruments.

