## PRÉCIS

Prevention of oral chronic graft versus host disease (GVHD) by topical agents is an attractive strategy because it would potentially avoid the adverse effects associated with systemic immunosuppression. Topically administered dexamethasone solution is a commonly used agent for the prophylaxis of oral inflammatory conditions including GVHD. However, the efficacy and systemic effects of topically administered dexamethasone solution are unknown. We therefore propose this trial designed to evaluate the efficacy and safety of topical dexamethasone solution for prevention of oral chronic GVHD in stem cell transplant recipients.

This pilot phase II study will follow a randomized, double-blind, placebo controlled, parallel group design. Consenting subjects who have undergone hematopoietic stem cell transplantation at the NIH Clinical Center and the surrounding transplant clinics will be randomized 50/50 to receive dexamethasone 0.01% solution or placebo as an oral rinse for 3 months starting 90-100 days post-transplant. Subjects will be evaluated monthly after the start of intervention. Diagnostic and research evaluations will include a complete oral examination, oral mucosal biopsy prior to the beginning of the intervention (day -7) and at the time of development of oral chronic GVHD or at the completion of intervention in the absence of clinical GVHD. We will measure serum dexamethasone levels and perform short cosyntropin (ACTH stimulation) test at the end of the 3 months of intervention or onset of clinically significant GVHD.

The primary objective of the study is to evaluate the safety and efficacy of topical dexamethasone 0.01% solution used as an oral rinse for prevention of oral chronic GVHD. Our primary endpoint will be the proportion of subjects that develop clinically significant (severity score 3 or higher) oral chronic GVHD after three months.

Secondary objectives will include the impact of oral chronic GVHD on the quality of life, characterization of the changes in tissue and salivary biomarkers associated with development of oral graft versus host disease, and measures of the effects of topical dexamethasone on hypothalamo-pituitary-adrenal axis. Secondary outcomes will include oral cavity specific quality of life as measured by OHIP-14 questionnaire, oral discomfort levels, improvement in general quality of life scores, and severity of oral chronic GVHD as measured by the site-specific GVHD scoring system.

---

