## 1.2 Secondary Objectives

- 1.2.1 To assess the incidence, risk factors and clinical characteristics of oral chronic GVHD.
- 1.2.2 To evaluate the impact of oral chronic GVHD on quality of life.
- 1.2.3 To evaluate the degree of systemic absorption of topical dexamethasone and its effect on adrenal cortical function.
- 1.2.4 To evaluate changes in salivary and plasma proteome associated with oral chronic GVHD.
- 1.2.5 To evaluate tissue kinetics and gene expression patterns of immune cells associated with the development of chronic oral GVHD and prophylaxis with topical dexamethasone.
- 1.2.6 To assess the predictive value of subclinical tissue changes on development of chronic oral and systemic GVHD and prognostic significance of these changes in terms of graft versus tumor effect.

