#### **6.1.2 Baseline assessments**

- Serum chemistry (Acute Care (Na, K, Cl, CO2, Creatinine, Glucose, and Urea Nitrogen), Mineral (Phosphorus, Magnesium, Albumin, and Calcium), Hepatic (Alk Phosphatase, ALT, AST, Total Bilirubin, and Direct Bilirubin), and Other (Total Protein, CK, Uric Acid, and LD) panel) done concurrently with post transplant monitoring
- Pregnancy test (females of child bearing potential)
- Serum cortisol level (results blinded to investigators)
- The 0-10 Scale for Oral Pain (see Appendix A)
- The 0-10 Scale for Oral Xerostomia (see Appendix A)
- GVHD Severity Scale (see Appendix B)
- Lichen Planus (Oral GVHD) Severity Scale (see Appendix C)
- Disease specific quality of life - OHIP-14 scale (ages 18 and older only-Appendix D)
- Oral photographs (Optional)
- Oral lesion documentation
- Buccal mucosal less than approximately 6mm punch biopsy (ages 18 and older only) (optional)
- Research blood sample collection
- Research saliva sample collection
- Growth chart (length for age, weight for age percentiles and body mass index for age percentiles, pre-pubertal children) (if a hand x-ray is available on parent transplant protocol, the results will be reviewed)

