### **6.2 On Study Drug Interim Assessments (1 month and 2 month phone contact)**

The NIH research team will contact the subject by clinical appointment, telephone or email at 1 month and 2 months (+/- 2 weeks) after initiation of study drug to inquire about adverse effects and the use of concurrent medications. Laboratory assessments done as part of their post transplant monitoring will also be reviewed when available. Subjects will be asked to return to clinic when clinically indicated and the following questionnaires will be completed at the time of contact.

- Concomitant meds (immunosuppressive, antimicrobial and analgesics)
- The 0-10 Scale for Oral Pain (see Appendix A)
- The 0-10 Scale for Oral Xerostomia (see Appendix A)
- Patient-assessed Global Scale (perception of changes in oral condition)

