### **6.3 End of Treatment Monitoring and Assessments (3 months)**

Subjects will be evaluated at the NIH at 3 months (+/- 7 days) after starting study medication with the following assessments:

- Interim assessment
- Blood pressure
- Concomitant meds (immunosuppressive, antimicrobial and analgesics)
- The 0-10 Scale for Oral Pain (see Appendix A)
- The 0-10 Scale for Oral Xerostomia (see Appendix A)
- Patient-assessed Global Scale (perception of changes in oral condition-Appendix A)
- GVHD Severity Scale (see Appendix B)
- Lichen Planus (oral GVHD) Severity Scale (see Appendix C)
- Disease specific QOL- OHIP-14 scale (ages 18 and older only) (Appendix D)
- Complete blood count (CBC with diff) – done concurrently with post transplant monitoring
- Serum chemistry (Acute Care (Na, K, Cl, CO2, Creatinine, Glucose, and Urea Nitrogen), Mineral (Phosphorus, Magnesium, Albumin, and Calcium), Hepatic (Alk Phosphatase, ALT, AST, Total Bilirubin, and Direct Bilirubin), and Other (Total Protein, CK, Uric Acid, and LD) panel) – done concurrently with post transplant monitoring
- Serum cortisol level (results blinded to investigators)
- ACTH stimulation test (Optional)
- Serum dexamethasone level (results blinded to the investigators)
- Buccal mucosal less than approximately 6mm punch biopsy ages 18 and older only (optional)
- Oral photographs (Optional)
- Oral lesion documentation
- Research blood sample collection
- Saliva sample collection
- Growth chart (length for age, weight for age percentiles and body mass index for age percentiles, pre-pubertal children) (if hand x-ray is available on parent transplant protocol, the results will be reviewed)

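### General quality of life is a stated secondary outcome and hypothesis, but the protocol names no instrument to measure it

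*Combined protocol and SAP*

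**What the plan says.** Two places promise general quality of life. The hypothesis in 8.1.2 covers both constructs: "prophylactic use of topical dexamethasone will improve oral health specific and general quality of life (QOL) as measured by the corresponding QOL instruments". The Précis sets them out as separate secondary outcomes: "oral cavity specific quality of life as measured by OHIP-14 questionnaire, oral discomfort levels, improvement in general quality of life scores". Section 1.2.2 gives a broader objective, "To evaluate the impact of oral chronic GVHD on quality of life", and names no instrument.

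The operative sections are narrower. The baseline list in 6.1.2 has "Disease specific quality of life - OHIP-14 scale (ages 18 and older only-Appendix D", and 6.3 and 6.5 repeat that entry with only trivial changes of wording. Section 8.4.4 defines OHIP-14 as a secondary endpoint on perceived oral health and restricts it to adults because it has been little studied in children. Section 8.5 compares quality-of-life scores between arms with the Wilcoxon test, and OHIP-14 is the only such score it names. It also says that adjustments will be made for age and other covariates, but it does not name the baseline OHIP-14 score.

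**The concern.** A hypothesis needs a measurement. Section 8.1.2 speaks of instruments in the plural, each corresponding to its construct, and the Précis separates general scores from OHIP-14. A reader therefore expects a second questionnaire with its own visits, scoring and analysis. If there is none, half of the quality-of-life hypothesis cannot be tested, and a listed secondary outcome will have no result when the trial is reported.

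**Working it through.** No figure in the plan needs recomputing here; the check is a cross-reading. The table sets out the patient-reported scales in each assessment list.

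| Assessment | General QOL instrument | OHIP-14 | Other patient-reported scales |
|---|---|---|---|
| 6.1.2 Baseline | none named | yes, adults | pain, xerostomia |
| 6.2 Months 1 and 2 | none named | no | pain, xerostomia, Global Scale |
| 6.3 Month 3 | none named | yes, adults | pain, xerostomia, Global Scale |
| 6.4 Remote follow-up (scales only if symptoms or signs are reported) | none named | no | pain, xerostomia, Global Scale |
| 6.5 End of study | none named | yes, adults | pain, xerostomia, Global Scale |

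Count: a general instrument is named in 0 of 5 lists; OHIP-14 is in 3 of 5.

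Next, the endpoints and analysis. Sections 8.4.1 to 8.4.6 cover pain and xerostomia, the severity scales, the Global Scale, OHIP-14, dexamethasone levels and adrenal function. None defines a general quality-of-life endpoint, and 8.5 adds none.

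Then, whether a listed scale could serve as the general one:

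- **OHIP-14.** The stem in Appendix D ties every item to trouble arising from the teeth, dentures or mouth. That includes item 13, on satisfaction with life. The visit lists call the scale disease specific, and the Précis lists it apart from general scores.
- **Global Scale.** Despite its name, Appendix A asks about the state of the mouth compared with a month earlier. Section 6.2 lists it as "Patient-assessed Global Scale (perception of changes in oral condition").
- **Appendix B and Appendix C.** These are lesion scores made by an examiner.

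Last, indirect evidence from the compensation table in 10.6. It pays for four unnamed questionnaires, three times each, the fourth for adults: 4 × 3 = 12 completions. If they are pain, xerostomia, the Global Scale and OHIP-14 at the baseline, month 3 and end-of-study visits, the lists give 3 + 3 + 2 + 3 = 11, because the Global Scale is not listed at baseline. The match is close but not exact. The table neither shows that a general instrument exists nor strictly rules one out.

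**The case against.** The strongest reply is that this is leftover wording. Visits, endpoints and analysis agree with one another; one phrase in 8.1.2 and one in the Précis are out of line. That stands, and it is why the point is small and is an inconsistency rather than a faulty design decision. It does not remove the point, because the two phrases still state an outcome that the trial cannot deliver.

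A second reply is that the data might come from the parent transplant protocol. Where this protocol borrows such data it says so, as for the screening assessments in 6.1.1 and the hand x-rays in 6.1.2 and 6.3. It says nothing similar about quality of life.

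A third is that baseline adjustment does not follow from the missing instrument, and that the covariate sentence in 8.5 could be read to allow it. Both parts are fair. The adjustment is a separate improvement, made while the same hypothesis is being restated, and it needs its own edit to 8.5. The existing sentence neither names the baseline score nor says how adjustment would be combined with a Wilcoxon test.

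Two stronger readings are tempting. A reader might infer that OHIP-14 would be presented as evidence on general quality of life. The documents do not support this: they label the scale disease specific, define it as perceived oral health, and list it apart from general scores. A reader might also count the absence of OHIP-14 in minors as part of the defect. That restriction is disclosed and justified in 8.4.4, and it has no bearing on whether a general instrument exists.

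**Conclusion.** The point holds as an internal inconsistency. General quality of life is hypothesised in 8.1.2 and listed in the Précis, and no instrument for it is named in 6.1.2 to 6.5, 8.4, 8.5 or the appendices. As designed, the trial cannot test or report it. The effect is confined to one secondary outcome; the primary endpoint, its analysis and the sample size are untouched. Removing the wording alone would change no result.

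The conclusion rests on two assumptions: that the text not available for review (front matter before the Précis and part of section 7) holds no further questionnaire schedule, and that the unnamed questionnaires in 10.6 are ones already listed. Neither can be verified, so the accurate statement is that no general instrument is named, not that none was ever administered.

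Adjusting OHIP-14 for baseline would use data the trial already collects. The gain in precision depends on the correlation between baseline and later scores, which the documents do not give, so no size is claimed.

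**What to change.** - In 8.1.2, delete *and general*. In the Précis, delete "improvement in general quality of life scores".
- Record general quality of life in the amendment and the final report as a planned outcome for which no instrument was specified. It should not disappear without comment.
- Restate the hypothesis as a difference between arms in OHIP-14 total score in adults.
- Amend 8.5 so that the OHIP-14 comparison is adjusted for the baseline OHIP-14 score, for example by rank-based ANCOVA, with the Wilcoxon test kept as supportive.

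Naming a general instrument now is the alternative. It would need visits, an age range, scoring and an analysis in sections 6, 8.4 and 8.5. It would not recover data from subjects who have already finished: the current text is Amendment AA of 2021, and 8.2 shows that an observed event proportion was already available at amendment R in 2016. Deletion with a record is the proportionate choice.

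The cost is small edits to the Précis, 8.1.2 and 8.5, and one unsupported claim given up. No new data or change to study conduct is needed.
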